7.2 Patient confidentiality

Each patient is assigned a unique patient study number at registration. In study documents, the patient's identity is coded by a patient study number. In some cases, date of birth is also listed. The local investigator will keep a subject enrolment and identification log that contains the code key, the personal identification data linked to each patient study number. This data is filed at the investigational site and should only be accessed by the investigator and the supporting site staff or by representatives of the sponsor-investigator or a regulatory agency, and only for monitoring visits or audits and inspections. The Information and Consent Form also explains that for data verification purposes an authorized regulatory authority, or an ethics review board may require direct access to parts of the hospital or practice records relevant to the study including patients' medical history.

7.3 Study insurance

Before the start of the study, the sponsor-investigator and principal investigator of each site will ensure that adequate insurance for patients is in place covering losses

due to death or injury resulting from the study, in accordance with applicable laws and regulations in each country where the trial is conducted. Adequate insurance for investigators and study staff will be ensured. The pharmaceutical company supplying drugs used in the study must have their own liability insurance.

7.4 Risk/benefit assessment

The patients eligible for this consolidation treatment are at higher risk of earlier relapse than average patients (see chapter 1.1), and positivity of PET-CT before maintenance treatment is the most important factor predicting overall survival. The selected patient group in this study is hence in need of better treatment and is a valid focus for a clinical study. Being in this situation, patients tend to desire more intensified therapy, and are in most cases willing to participate.

The KRd regime is proved safe and efficient for 18 consecutive cycles in relapsed patients (5), and has also recently demonstrated safety in extended treatment after transplant. As such, there is not expected to be any new safety issues with four cycles in this population. The relapse treatment has been with a lower carfilzomib dose of $27\text{mg}/\text{m}^2$, because the population is more prone to adverse events. The KRd regime has also been tried in several smaller phase 1 and phase 1/2-studies in newly diagnosed multiple myeloma, both in young and elderly populations. In this situations $36\text{mg}/\text{m}^2$ is a well-tolerated and effective regime, without new, unexpected or alarming safety problems.

However, intensified therapy will always come with a certain increase in adverse events. Patients will be informed about this. There are also practical strains with participating in studies, with more cumbersome examinations and for some patients a longer transport to the study center. The patients will also be informed about this, and that they can withdraw at any given time point.

Overall, the risk-benefit assessment for patients in this study looks acceptable.

7. INVESTIGATIONAL PLAN – STUDY DESIGN

This is an investigator initiated, academic, non-randomized, open-label multicenter study for consolidation in patients with multiple myeloma after standard first line treatment.

CONPET vs 14, 24th October 2018

After a standard induction regime with ASCT, patients can be included in the study. A PET-CT will be performed, patients with a negative PET result will go out of the study, with a strong recommendation of standard-of-care treatment, as specified below. Patients with a positive PET result will receive four cycles of KRd followed by standard-of-care treatment with lenalidomide maintenance 10-15mg once daily

A new PET-CT-evaluation will be performed after completed consolidation. At inclusion in the study, MRD samples will be taken from all patients. We will repeat these samples after completed consolidation. The goals of the study are to evaluate what proportion of patients are PET-positive after standard first line treatment and how many of these can become PET-negative after KRd consolidation. The study will explore the dynamics of MRD status in this setting, and the correspondence between these two methods. Review of PET-CTs will be central and blinded.

The PET-CT-negative group will have long time follow up through their local doctor for PFS and OS

The study is a phase 2 study, with 50 PET-positive patients, to show the feasibility, safety and efficacy of this design.

Inclusion of patients will continue until 50 PET-positive patients have been included.

8. STUDY POPULATION

8.1 Inclusion criteria

Each patient must meet all the following inclusion criteria to be enrolled in the study:

1. At least 18 years of age, with at least 6 months expected survival.
2. Prior confirmed diagnosis of multiple myeloma (2014) (16).
3. Received standard first line treatment with at least a very good partial response (VGPR), according to IMWGs criteria . Standard first line treatment is defined as

VRD, VTD or VCD followed by ASCT with or without lenalidomide maintenance initiated (Patients where the monoclonal component or dFLC increases during the period from best response to screening can be included if there is no progressive disease.)

4. Patients must be carfilzomib naïve.
5. A positive PET-CT result from central reviewer in the screening period

6. Successful FISH evaluation performed with available results
7. Voluntary written consent must be given before performance of any study related procedure not part of standard medical care, with the understanding that the patient may withdraw consent at any time without prejudice to future medical care.
8. Females of childbearing potential (FCBPs) must have a confirmed negative serum pregnancy test within the 7 days prior to inclusion
9. FCBPs and male subjects who are sexually active with FCBP must agree to use highly effective concomitant methods of contraceptive during the study and for 30 days following the last study drug dose. Male subjects must use contraception and refrain from donating sperm for at least 90 days after the last dose of carfilzomib.
10. Eastern Cooperative Oncology Group (ECOG) performance status 0-2. In patients >75 years of age, performance status 0-1.
11. Patients must meet the following adequate organ and bone marrow function within 21 days prior to inclusion:
 - Absolute neutrophil count (ANC) $\geq 0,5 \times 10^9/L$ and platelet count $35 \times 10^9/L$. Platelet transfusions to help patients meet eligibility criteria are not allowed within 3 days before study enrollment. Granulocyte growth factors are allowed to meet the inclusion criteria.
12. Patient must be willing and able to adhere to the study schedule and other protocol requirements.

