7.1 Informed consent

Written informed consent of patient is required before any study related procedure. The investigator should provide enough time for patient to discuss about all details of the study. All questions concerning the study will be answered to the satisfaction of the patient before possible obtaining of consent. The content of the patient information letter, informed consent form and any other written information provided to patients will be in compliance with ICH-GCP and other applicable regulations and should be approved by the Ethics Committee before use. Whenever new important information relevant to the patient's consent will be available, the patient information letter, informed consent and any other written information will be revised. Any revised informed consent form and written information should be approved by the Ethics Committee before use. The patient should be informed in a timely manner if new information becomes available that might be relevant to the patient's willingness to continue participation in the study.

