10. END OF STUDY

Inclusion in the study ends when 50 patients have had positive initial PET-CT results. After progressive disease, patients will be followed by telephone for overall survival. Patients with negative PET-CT results will be followed by telephone/fax for progressive-free survival and overall survival every second month (± 7 days).

The study will end with last patients last visit. There will be a post-study follow-up for overall survival in all patients, both with initial PET-CT positivity and negativity.

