15. STATISTICAL CONSIDERATIONS

16.1 Sample size determination

The objective of the study is to describe the proportion of patients still PET-positive after standard first line treatment in the Nordics, and to describe how many of these can become PET-negative after consolidation with KRd. The study is a phase 2 study looking at the feasibility and safety of this approach. Fifty PET-positive patients is considered acceptable to achieve this objective, see Table below for precision of the estimates with different proportions. We anticipate a 50% PET- CT-positivity after first line treatment in the total population, which amounts to 100 pts screened with PET-CT initially. 50 PET-CT+ patients will be included.

| Proportion | Confidence Interval |
|------------|---------------------|
| 0.1 | (0.043 - 0.214) |
| 0.2 | (0.112 - 0.330) |
| 0.3 | (0.191 - 0.438) |
| 0.4 | (0.276 - 0.538) |
| 0.5 | (0.366 - 0.634) |
| 0.6 | (0.462 - 0.724) |
| 0.7 | (0.562 - 0.809) |
| 0.8 | (0.670 - 0.888) |
| 0.9 | (0.786 - 0.957) |

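### The protocol contradicts itself on whether a patient enters the study before or after the PET-CT result, which leaves the PET-positive proportion open to selective registration

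*Protocol*

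**What the plan says.** Two accounts of study entry stand side by side in the protocol.

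**Entry after a positive scan.** Section 8.1 opens with "Each patient must meet all the following inclusion criteria to be enrolled in the study", and criterion 5 on that list is "A positive PET-CT result from central reviewer in the screening period". Section 16.1 uses the same sense of inclusion: "100 pts screened with PET-CT initially. 50 PET-CT+ patients will be included".

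**Entry before the scan.** Section 7 (Investigational plan) says that after induction and ASCT "patients can be included in the study. A PET-CT will be performed, patients with a negative PET result will go out of the study". It also takes MRD samples from all patients at inclusion. Section 10 adds: "Patients with negative PET-CT results will be followed by telephone/fax for progressive-free survival and overall survival every second month".

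The consent wording splits too. Section 7.1 says: "Written informed consent of patient is required before any study related procedure". Criterion 7 in section 8.1 is narrower: "Voluntary written consent must be given before performance of any study related procedure not part of standard medical care".

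The PET-positive proportion after standard first-line therapy is named as a primary endpoint in the synopsis and in section 16.2, and it is part of the primary objective in section 6.1.

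**The concern.** A proportion needs a denominator fixed without knowledge of the result. Under section 7 the denominator is everyone included and then scanned. Under section 8.1 a PET-negative patient cannot be enrolled at all. Where a site regards the PET-CT as standard care, criterion 7 also allows the result to be known before the patient is approached. A site that treats 8.1 as its working eligibility list could therefore register the positives it wants to treat and record negatives only in part.

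Missing negatives shrink the denominator and leave the numerator alone, so the error runs upward. The endpoint is meant to describe how often patients remain PET-positive after first-line treatment in the Nordic countries, and the estimate would then partly reflect who was approached.

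**Working it through.** **1. The text, step by step.**

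| Question | One answer | Other answer |
|---|---|---|
| Is a PET-negative patient a study patient? | No (8.1, criterion 5) | Yes, until the result is known (7), with follow-up afterwards (7, 10) |
| May the scan come before consent? | Yes, if it is standard care (8.1, criterion 7) | No, if it is a study procedure (7.1) |
| When is the first MRD marrow taken? | At inclusion, from all patients (7) | Day 1 of Cycle 1, none at screening (Study Procedures table) |

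The third row matters because baseline marrow sampling might have served as a record of everyone included. In the Study Procedures table it falls at a visit that PET-negative patients do not reach.

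**2. The plan's own figure.** Section 16.1 expects 50% positivity and 50 positives: 50 / 0.50 = 100 scanned. This reproduces. Section 4 (Study rationale) cites 30 to 40% positivity in earlier data. At those rates the number scanned would be 50 / 0.40 = 125 to 50 / 0.30 = 167.

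**3. Effect of unregistered negatives.** Let p be the true positive proportion and f the share of PET-negatives never registered, with all positives registered. The expected estimate is

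p / [p + (1 − p)(1 − f)].

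The protocol gives no value for f, so the values below are assumptions. The 35% column is the midpoint of the cited 30 to 40%, and 50% is the value anticipated in 16.1.

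| Negatives not registered | p = 30% | p = 35% | p = 40% | p = 50% |
|---|---|---|---|---|
| 0% | 30.0% | 35.0% | 40.0% | 50.0% |
| 10% | 32.3% | 37.4% | 42.6% | 52.6% |
| 20% | 34.9% | 40.2% | 45.5% | 55.6% |
| 50% | 46.2% | 51.9% | 57.1% | 66.7% |

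For p = 35%: 0.35 / (0.35 + 0.65 × 0.8) = 0.35 / 0.87 = 0.402, and 0.35 / (0.35 + 0.65 × 0.5) = 0.35 / 0.675 = 0.519.

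**4. Scale against sampling error.** With 50 positives among 143 scanned (50 / 0.35), the Wilson 95% interval is 0.276 to 0.431, about ±8 points. A 20% loss of negatives shifts the estimate by 5.2 points, which is inside that margin. A 50% loss shifts it by 16.9 points, about twice the margin. The Wilson interval around the shifted value would be 0.420 to 0.616, which excludes the true 35% and sits around the anticipated 50%, so the error could pass for confirmation.

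**The case against.** The strongest reply is that the protocol as a whole clearly means to capture negatives. Section 16.1 plans about 100 scans, section 7 provides long-term follow-up of the PET-negative group, and section 10 follows them every second month. None of that is possible unless negatives are recorded, so a site registering only positives would breach sections 7 and 10. Section 7.1 has no standard-care exception, PET-CT is a scheduled screening procedure, criterion 5 requires a central read, and the PET/CT background section says routine use in follow-up is not yet recommended. Nothing in the protocol calls this scan standard care. The separate PET-CT protocol (Appendix 6) is not available and might say more.

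Most of this stands, and it rules out one stronger reading: a reader might infer that PET-negative patients need never be registered, or that the endpoint is biased as designed. The documents do not support that. What remains is that follow-up reaches only the negatives a site has identified, and no section says when or how they are registered.

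A reader might also infer an opposite, downward bias: positives who fail another criterion after the scan drop out of the 50 included while the negatives all count. That needs an estimator of 50 included over all scanned, which the protocol never states. Section 10 stops inclusion on positive initial scans, which points the other way. Such patients have a known positive scan, so counting all positive scans over all scans repairs the error.

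Finally, this is a descriptive single-arm phase 2 trial, and the conversion endpoint among treated patients is untouched. That is correct and limits the reach of the point to the first primary endpoint.

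**Conclusion.** The contradiction between sections 7, 7.1, 8.1 and 10 and the Study Procedures table on the point of entry is real and bears on a primary endpoint. Its consequence is a conditional upward risk. If a site follows 8.1 literally and records negatives incompletely, the PET-positive proportion is overstated, and later analysis cannot recover patients who were never registered. At an assumed true 35%, losing 20% of negatives gives about 40% and losing 50% gives about 52%. Both loss rates are illustrations without a source in the protocol, and the smaller shift lies within sampling error. The point should be settled in the protocol because it concerns who is recorded, which an analysis plan cannot change afterwards.

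**What to change.** Define entry in two steps.

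1. **Registration**, completed before the PET-CT result is known: written consent plus the disease and first-line-treatment criteria (age, diagnosis, VGPR or better after VRD, VTD or VCD and ASCT, no contraindication to PET-CT).
2. **Treatment entry**: criterion 5 and the criteria that concern KRd treatment, moved from the enrolment list to this step with their content unchanged.

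Align criterion 7 with section 7.1, and reconcile the timing of the first MRD sample between section 7 and the Study Procedures table. Estimate the PET-positive proportion as all centrally read positive scans over all registered patients with a central read, whether or not a positive patient later fails a treatment-entry criterion. Keeping the KRd-fitness criteria out of step 1 avoids testing patients who will not be treated, and avoids narrowing the estimate to KRd-eligible patients.

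The cost is one amendment and a registration form, with no scans beyond those already planned. The small downside is that patients whose PET-CT result was known before registration do not count for this endpoint.

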8.2 Exclusion criteria

Patients meeting any of the following exclusion criteria are not to be enrolled in the study:

1. Change of first line treatment because of stable or progressive disease.
2. Female patients who are lactating or have a positive serum pregnancy test during the screening period.
3. Major surgery within 28 days before enrollment.
4. Radiotherapy within 14 days before enrollment. Glucocorticoid therapy within the 14 days prior to inclusion that exceeds a cumulative dose of 160 mg dexamethasone or 1000 mg prednisone.

5. Patients who started treatment more than 12 month before screening
6. Central nervous system involvement.
7. Uncontrolled heart disease, including congestive heart failure (NYHA III-IV), uncontrolled angina pectoris, uncontrolled conduction abnormalities, acute diffuse infiltrative pulmonary disease, pericardial disease or myocardial infarction within 6 months prior to enrollment
8. Active hepatitis B or C infection or known human immunodeficiency virus (HIV) positivity.
9. Any other serious medical or psychiatric illness that could, in the investigator's opinion, potentially interfere with the completion of treatment according to this protocol.
10. Known allergy to Captisol (a cyclodextrin derivative used to solubilize carfilzomib) or to any of the study medications, their analogues, or excipients in the various formulations of any agent.
11. Contraindication to dexamethasone or any of the required concomitant drugs or supportive treatments, including hypersensitivity to antiviral drugs, or intolerance to hydration due to pre-existing pulmonary or cardiac impairment.
12. Another active malignancy. Patients with non-melanoma skin cancer or carcinoma in situ of any type are not excluded if they have undergone complete resection.
13. Patients that have previously been treated with carfilzomib.
14. Primary plasma cell leukemia, systemic AL amyloidosis, Waldenström's macroglobulinemia, POEMS syndrome.
15. Pleural effusions requiring thoracentesis within the 14 days prior the inclusion.
16. Ascites requiring ascites puncture within the 14 days prior to inclusion.
17. Previous allogeneic transplantation
18. Uncontrolled hypertension or uncontrolled diabetes despite medication
19. Contraindication to PET-CT

20. Not expected to tolerate full dose KRd

9. DISCONTINUATION OF SUBJECTS FROM TREATMENT

Patients will be informed that they have the right to withdraw from the study at any time for any reason, without prejudice to their medical care. The investigator has also the right to withdraw a patient from the study for any of the following reason.

Adverse event

Protocol violation

Loss to follow-up

Progressive disease

Study termination

If the responsible physician believes a change of therapy would be best for the patient

No compliance of the patient

Pregnancy

Death

Patients who are withdrawn from study will not be replaced. At the time of withdrawal, all study procedure outlines for the end of visit should be completed. The primary reason for patient's withdrawal from the study should be recorded in the source documents and CRF. When the study is over or the patient withdraws for any reason, the patient will be treated according to standard-of-care in the Scandinavian countries.

10. END OF STUDY

Inclusion in the study ends when 50 patients have had positive initial PET-CT results. After progressive disease, patients will be followed by telephone for overall survival. Patients with negative PET-CT results will be followed by telephone/fax for progressive-free survival and overall survival every second month (± 7 days).

The study will end with last patients last visit. There will be a post-study follow-up for overall survival in all patients, both with initial PET-CT positivity and negativity.

11.1 Stopping rules/discontinuation criteria/serious breach

The Investigator may discontinue the study for medical reasons, prior to inclusion of the intended number of patients. At the discretion of the Sponsor-investigator, the study may be discontinued for other reasons, prior to inclusion of the intended number of patients. A premature discontinuation of the study can be decided by the Sponsor in the following cases:

- The study is not conducted in accordance with the procedures defined in the approved protocol (i.e. protocol deviations, failure to ensure the quality of the data collected)
- If additional information which results in changes in the risk/benefit assessment becomes available
- The discovery of an unexpected and significant or unacceptable risk to the patients enrolled in the study.
- Failure of the Investigators to enter patients at an acceptable rate in the study as a whole

The Ethics Committee(s) and Regulatory Authorities will be informed by the sponsor about a premature discontinuation of the study. Reporting will be done in accordance with the required timelines.

11. TREATMENT

12.1 Study Drug Administration Schedule

28-day cycle

| Cycles 1 | | | |
|-----------------|----------------------|--------------|--------------|
| Agent | Dose/day | Route | Days |
| Carfilzomib | 20 mg/m ² | IV | 1, 2 |
| | 36 mg/m ² | IV | 8, 9, 15, 16 |
| Lenalidomide | 25 mg | Oral | 1-21 |
| Dexamethasone | 40 mg | Oral | 1, 8, 15, 22 |

| Cycles 2-4 | | | |
|-------------------|----------------------|--------------|--------------------|
| Agent | Dose/day | Route | Days |
| Carfilzomib | 36 mg/m ² | IV | 1, 2, 8, 9, 15, 16 |
| Lenalidomide | 25 mg | Oral | 1-21 |
| Dexamethasone | 40 mg | Oral | 1, 8, 15, 22 |

During Cycles 1-4, administration of carfilzomib can be adjusted within the following window:

Day 1 -0/+2 days

Day 2 \pm 0

Day 8 -1/+1

Day 9 \pm 0

Day 15 -1/+1

Day 16 \pm 0

12.2 Carfilzomib administration

Patients will receive IV prehydration prior to the first carfilzomib infusion during cycle 1. Prehydration will consist of 250 to 500 ml normal saline or other appropriate IV fluid.

Thereafter, carfilzomib prehydration should only be administered if the patient's condition and/or risk factors require hydration. Carfilzomib will be administered as an IV infusion over 30 minutes.

Carfilzomib for injection is supplied as a lyophilized parenteral product in single-use vials packaged in multi-vial cartons. Institutional pharmacies will be supplied with vials with adequate study labeling. Study treatments should be stored in a securely locked area with access limited to appropriate study personnel. Carfilzomib must be stored at 2°C to 8°C in a refrigerator. Carfilzomib vials must be kept in cartons to protect from light until ready for reconstitution. Once carfilzomib is reconstituted and inspected, the clear solution may be stored between 2°C to 8°C for up to 24 hours. Once reconstituted, carfilzomib must be used within 4 hours if not refrigerated and within 24 hours if it has been stored in a light-tight refrigerator. The lyophilized product is reconstituted with sterile water for injection, to a final carfilzomib concentration of 2.0 mg/ml prior to administration. The dose will be calculated using the patient's body surface area (BSA) at baseline. Patients with a BSA $>$ 2.2 m² will receive a dose based upon a BSA of 2.2 m². Dose adjustments must be made for weight gains/losses of \geq 20% of baseline body weight.

Mechanical infusion pumps are recommended but gravity-dependent infusions are permitted if the 30-minute infusion duration can be reliably maintained. Carfilzomib

infusion must occur at a facility capable of managing hypersensitivity reactions. Patients will remain at the investigational site under observation for at least one hour following each infusion of carfilzomib in cycle 1. Carfilzomib must be administered via a dedicated IV line. If a permanent infusion device (e.g. Porta-Cath), is used for infusion the line must be flushed with a minimum of 20 ml of glucose prior to and following carfilzomib infusion.

